## VI. Study Procedures/Study Design

**Group 1: Usual care.** Participants in this group will receive standard hospice care and bereavement support according to the policy of each hospice agency. We considered using an attention match control but chose “usual care” instead, as prior research demonstrated that using attention match control in a behavioral randomized trial is problematic, especially for outcomes such as depression (our primary outcome of interest) and anxiety. This literature advocates that controlling for attention is not necessary and counterproductive in some behavioral intervention trials. Once assigned to an arm, the participant remains in that arm for the entire study, from active caregiving through bereavement. We will not randomize a second time at bereavement. Control group participants will complete study measures electronically through the REDCap system at the same intervals as the intervention group.

**Group 2: Caregiver Speaks intervention group.** Participants in this group will receive usual care plus the Caregiver Speaks intervention. They will participate in a Facebook group to share their photos and personal stories. During the initial zoom meeting, a research staff person will 1) train caregivers how to set-up and use Facebook, if needed, 2) discuss elements of their story and identify artifacts they may wish to feature in their photo-elicitation process, and 3) enroll them in the pre-bereavement caregiver private Facebook group. Caregivers will participate in this group until the PLWD dies, at which time they will transition (one month) into a bereavement focused group. The bereavement group will include the same components, but the focus of the photos and conversation will be on bereavement. Table 1 provides a summary of the study and intervention participation, as well as the data collection schedule. We will provide caregivers a printed reference guide for using Facebook, including group rules and common Facebook terms, based on materials we have used extensively in our preliminary work.

In an effort to increase retention of participants, the interventionist will now add a follow-up/technical assistance phone call with each NEW intervention participant after they have completed one full week of the intervention to assess the following:

- a. whether or not there are barriers to accessing/using Facebook.
- b. whether or not caregivers are able to share photos.
- c. whether or not they know how to set up their notifications to alert them of new posts in the group.
- d. whether or not they understand what to share in the group.

**Table 1 Summary of Study/Intervention Participation for Caregiver Speaks**

Time	Study/Intervention Procedures
Recruitment and Randomization	Flyer given to interested participants by hospice admissions staff, consent given for research staff to contact participant. In addition to that we will send recruitment information packets to some referrals by mail. We will send declines as referrals to another study. Encode (1R01AG069936). Initially consented participants will be given a brief explanation of study-by-study staff and asked

	for verbal consent to participate. Randomization occurs. Zoom meeting (orientation) scheduled.
Zoom (orientation) meeting	Instructions given to intervention group for Facebook and photo-elicitation procedures
Monthly (pre-bereaved caregiver Facebook group)	Research staff will provide ongoing facilitation and encourage discussion of photos and caregiver experiences based on monthly themes. Research staff will encourage participants to post weekly.
1-month bereavement transition	Once bereaved, caregivers will have one month to transition into the bereavement group. Research staff will 1) walk them through the steps of joining the bereavement group, 2) give instructions, and 3) conduct a brief, semi-structured, qualitative interview.
Monthly (bereaved caregiver Facebook group)	Research staff will facilitate discussion of photos based on monthly themes. This will continue up to ~180 days (6 months) after the death of their loved one. Research staff will encourage participants to post weekly.
Study exit	Termination and follow-up: participants will terminate from the group, and will complete 180-day survey and follow-up interview.

The Facebook group will possess the highest privacy level Facebook offers (secret group). Only consented users can search for secret groups; internet searches cannot find them. Membership in a secret Facebook group requires an invitation by a group administrator. Hospice family caregiver participants will be encouraged to log in at least once a week to read content, post photos, and share their stories with other caregivers.

PI [name] (expert in storytelling and photo-elicitation) and Co-I [name] (photo-elicitation expert) will train and supervise a research team member to serve as the primary Facebook moderator. The moderator will monitor the interactions and discussions among participants daily. Drs. [name] and [name] and two additional staff will support the facilitation when needed. Based on our pilot work and effectiveness trial (R24HS022140) of photo-elicitation storytelling and Facebook groups, one full-time facilitator will be responsible for up to 100 group members at a time.

Our preliminary work demonstrated that Facebook group members participated more when the moderator asked them to post pictures that captured their experiences, asked questions about the photos, and engaged other members in discussion about the photos. Therefore, the moderator will ask active caregivers to post photos representing their caregiving experiences, their caregiving process, and their meaning structures (e.g., this is what my family dynamic looks like now, while actively caring for my ill family member; this is how my life changed when I assumed the caregiving role; these are the types of things we do as a family now that I am actively caregiving) as related to the month's theme. The moderator will encourage active discussion and posting, weekly (related to the theme). In the bereavement group, the same moderator will ask members to share photos capturing their experiences with death and loss and their post-loss meaning structures (e.g., this is how my family dynamic has changed since the loss; I am now able to do these things again post-loss; this is how my life changed post-loss). The photo-elicitation process is described below.

Caregivers who express a need for additional psychological support will be referred to a hospice social worker (before their family member dies) or hospice bereavement counselor (during bereavement). Although we have found Facebook to be an effective platform where members deliver stories and engage with others with similar experiences, important ethical issues are inherent with this approach. This group is designed for research purposes only. Any caregivers who demonstrate crisis or express intent to harm themselves or others will be dealt with respectfully by the qualified research staff person monitoring the group. Supportive materials (e.g., suicide crisis hotline phone numbers, national information regarding dementia caregiver support) will be made available to any caregiver who expresses interest or demonstrates a need.

Photos are the primary medium through which participants will engage with other group members, responding to the prompts described by the facilitator. Before their loved one dies, caregivers will be asked to take photographs that they feel best capture their daily caregiving and share them with other caregivers in the pre-bereavement Facebook group. The primary group moderator will ask caregivers to focus their photo-taking and discussion on their pre-loss meaning structures (including their pre-caregiving lives) and how this has changed over the course of the illness. For example, caregivers may capture their daily activities caring for their family member, their perceptions of themselves and their interpersonal relationships (including how these changed when they assumed the caregiver role), and how caregiving affects their views of the future and their world. Caregivers who enter the bereavement phase of the study will be asked to take photographs capturing their post-loss meaning structures (e.g., how their sense of self has changed in bereavement, re-examined priorities for life, relationships with the living and continued bonds with the dead, and how their views of the world and future have changed). Members will be asked to discuss these things with others in the bereavement group.

See Table 2 (below) for data collection timing, measures (including psychometric properties), and our specific aims, which focus on key aspects of our conceptual model. Our planned data collection frequency mirrors procedures in our other clinical trials in hospice, allowing us to get measures closest to the patient's death and also through a significant amount of time in bereavement.

**Table 2: Aims, Hypotheses, and Associated Measures**

*Pre-bereavement measures collected at baseline, 14, 30, 90, and 150 days (follow-up data collection post 150 days will occur every 6 weeks until participant transitions to bereavement). Post-death measures collected at transition, 14, 30, 90, 150 and 180 days. During study wind down, participants will complete their final data collection measure based on where they are at in the intervention (e.g., if a participant is on day 90 of 150, they will complete day 90 survey as their final measure).*

Specific Aim	Hypotheses (H) and Research Questions (RQ)	Instruments and Variables	Description
Aim 1: Determine the efficacy of the Caregiver Speaks intervention in reducing depression and anxiety among hospice family caregivers of PLWD.	RQ1: What is the effect of the Caregiver Speaks intervention on caregivers' depression, anxiety (outcomes of interest)? H1a: Family caregivers receiving the intervention will	Primary Outcome: Depression Patient Health Questionnaire (PHQ-9) Secondary Outcome: Anxiety Generalized	PHQ-9: a 9-item screening tool and severity measure for depressive mood.  Internal Consistency: .87 

	
report lower depression and anxiety (outcomes of interest), which is facilitated by higher social support (mediating variable) than those in the control group during active caregiving.
 
H1b: Family caregivers receiving the intervention will report lower depression and anxiety (outcomes of interest), which is facilitated by higher social support (mediating variable) than those in the control group during bereavement.
 
H1c: the intervention group, family caregivers with higher baseline depression scores will experience a larger reduction in depression compared to those with less depression at baseline.
	
Anxiety Disorder (GAD-7)
 
Mediating Variables: Social Validation & Growth: Social Meaning in Life Events Scale –Social Validation SMILES-SV
 
Integration of Stressful Life Experiences Scale Short Form (ISLES-SF)
 
Caregiver Quality of Life Index (CQLI-R)
	
GAD-7: a 7-item screening tool and severity measure for generalized anxiety. Internal Consistency: .89
 
SMILES-SV: a 9-item tool for measuring social validation and meaning-making during stressful life events. Internal Reliability: .84
 
ISLES-SF: a 6-item measure that assess meanings made of stress during bereavement.
 
CQLI-R: a 4-item scale that measures physical, social, emotional, and financial quality of life among active caregivers.

Aim 2: Examine the effect of the Caregiver Speaks intervention on grief intensity among bereaved hospice family caregivers of PLWD
	
H2: Bereaved family caregivers receiving the intervention will report lower grief intensity (outcome of interest) than those in the control group.
	
Secondary Outcome: Grief Intensity Texas Revised Inventory of Grief (TRIG)-Present Scale
	
TRIG-Present: a 13-item scale measuring present grief among bereaved individuals. Internal Consistency: .86

Aim 3: Describe how caregivers make meaning of their caregiving and bereavement experiences
	
RQ2: In what ways do active caregivers find meaning as reflected in their FB posts?
	
Caregiver Photos, Discussion of Photos via Facebook Group, Post-intervention
	
Qualitative data triangulation and mixed methods analysis.

	RQ3: In what ways do bereaved caregivers find meaning as reflected in their FB posts? RQ4: In what ways does the social support in an online group facilitate meaning making?	Interviews, SMILES-SV, ISLES-SF, and Grief intensity scale	
--	--	---	--

### **Data Analysis Plan:**

**Statistical Assumptions.** We will examine linearity and homoskedasticity by calculating and plotting residuals and Cook's distance for all models. Where data are missing, we will use the Last Observation Carried Forward (LOCF) missing data imputation technique, given that < 30% of data were missing for any particular subject in our prior work. If the proportion of missing data is higher, we will use regression based multiple imputation. Little's MCAR test (missing completely at random) will be used to test that missingness is in no way related to the intervention. Because the sample size is relatively large, we expect that known and unknown confounders will be distributed evenly among the two randomized groups. Additional confounders will only be introduced as covariates if we find evidence of imbalance between groups at baseline. We acknowledge that this study is not powered to detect small interaction effects.

We will test whether randomization created balanced groups by comparing baseline measures and demographic characteristics, using chi-square or t-test analysis for categorical or continuous variables, respectively. Variables that differ significantly between groups will be included in regression models as potential confounders. We will include time from study enrollment to the last observation as a covariate, as well as hospice agency. We will report estimates with 95% confidence intervals. To draw inferences from our study for the likely benefit to an equivalent population, where the intervention under trial is a model of service delivery, all analyses of outcomes will be by intention-to-treat. The intention-to-treat analysis, consistent with the objectives of a pragmatic trial, will minimize the influence of "informative missingness" of the data and preserve groups' comparability.

**Statistical Analysis.** H1a: Family caregivers receiving the intervention will report lower levels of depression and anxiety (outcomes of interest), which is facilitated by higher social support (mediating variable) than those in the control group during active caregiving.

H1b: Family caregivers receiving the intervention will report lower levels of depression and anxiety (outcomes of interest), which is facilitated by higher social support (mediating variable) than those in the control group during bereavement.

We will examine differences between longitudinal profiles of the two study groups for each of the outcomes (PHQ-9, GAD-7, and grief intensity). We will use linear mixed effect repeated measurement (MMRM) (see model below). This will allow us to draw inferences about how our outcome measures (PHQ-9, GAD-7 and grief intensity) change over time ( $\text{slope} = \beta_{(1,T)}$  and  $\beta_{(1,C)}$ ) between the two study groups. Mixed models are able to accommodate differing numbers of measurements at varying time intervals for participants. Additionally, we will examine how social support mediates our outcomes of interest (depression, anxiety, and grief intensity). As described above, we will also include covariates where indicated.

$$\begin{aligned}
 Y_{ij} &= \beta_{-}(0,T) + \beta_{-}(1,T) t_{ij} + b_{-}oi + e_{-}ij && \text{for Treatment group} \\
 &= \beta_{-}(0,C) + \beta_{-}(1,C) t_{ij} + b_{-}oi + e_{-}ij && \text{for Control group}
 \end{aligned}$$

Where  $Y_{ij}$  represent the depression/anxiety score of the  $i^{th}$  subject at the  $j^{th}$  time,  $\beta_{-}(1,T)$  and  $\beta_{-}(1,C)$  represent the slopes for the treatment and control group respectively with intercepts that vary about the respective mean intercepts  $\beta_{-}(0,T)$  and  $\beta_{-}(0,C)$ .

H1c: Among the intervention group, family caregivers with higher baseline depression scores will experience a larger reduction in depression compared to those with less depression at baseline.

A multiple linear regression model will be used as for H1a above to examine the modifying effect of baseline PWBS score. If the  $\beta_2$  coefficient is negative and statistically significant, we will conclude that the effects of the Caregiver Speaks intervention are conditional on baseline perceptions after adjusting for duration of caregiving (time).

$$\text{Last post-baseline Anxiety/depression} = \beta_0 + \beta_2 * [\text{baseline anxiety/depression}] + \beta_3 * [\text{time}]$$

H2: Bereaved family caregivers receiving the intervention will report lower grief intensity (outcome of interest) than those in the control group.

A linear mixed effect model similar to those used for H1a and H1b will be used to examine H2, where the  $Y_{ij}$  will represent the grief intensity score for a subject of the  $i^{th}$  subject at the  $j^{th}$  time.

**Subgroup Analysis.** We will analyze several subgroups to identify unique attributes that might influence outcomes. Our subgroups are 1) hospice agency, to reflect different organizational structures, 2) older age, gender, race & ethnicity, which might influence use or understanding of Facebook, 3) Caregiver relationship to and residence with the patient, which could affect the meaning and amount of burden and 4) Time from enrollment to last observation, which reflects intervention dose, and 5), co-morbidities in patients, which may impact caregiving outcomes.

**Qualitative Analysis.** See Table 3 (below) for a detailed qualitative analysis plan. We will enter all photos, qualitative Facebook data, and transcribed interviews into qualitative coding software (Dedoose) for triangulation (use of multiple data sources to ensure a rich and robust dataset) and thematic analysis.

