# **Caregiver Speaks Data Analysis Plan**

**January 5, 2019**

**NCT04103580**

## Data Analysis

### Statistical Assumptions

We will routinely test assumptions of linearity, independence and homoskedasticity by calculating and plotting residuals and Cook's distance for all models. Where data are missing, we will substitute the mode for categorical data and the median for continuous data, given that <0.5% of data were missing for any measure in our preliminary trial. If the proportion of missing data is higher, we will use multiple imputation. In the analysis for H1a, we will use the final measure provided by caregiver before patient death, and for H1b we will use the final measure during bereavement. Because the sample size is relatively large, we expect that known and unknown confounders will be distributed evenly among the two groups. We acknowledge that this study is not powered to detect small interaction effects. Additional confounders will only be introduced as covariates if we find evidence of imbalance between groups at baseline.

We will test whether randomization created balanced groups by comparing baseline measures and demographic characteristics, using chi-square or t-test analysis for categorical or continuous variables, respectively. Variables that differ significantly between groups will be included in regression models as potential confounders. To compare outcomes for our hypotheses, we will use the last available measure post-baseline and prior to death or the end of the study and last measure during bereavement. This is a last-observation analysis.

Carpenter and Kenward argue that, in such analyses, time to this event should be taken into account. Therefore, we will include time from study enrollment to the last observation as a covariate. We will report estimates with 95% confidence intervals. To draw inferences from our study to the likely benefit to an equivalent population where the intervention under trial is a model of service delivery, all analyses of outcomes will be by intention-to-treat. The intention-to-treat analysis, consistent with the objectives of a pragmatic trial, will minimize the influence of "informative missingness" of the data and preserve groups' comparability.

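### Protocol and SAP prescribe incompatible missing-data rules, the SAP's printed equation does not match its mixed model, and LOCF is unnecessary for outcome scores in a mixed model

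*Protocol*

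**What the plan says.** **Missing data, protocol** (section VI, Data Analysis Plan, Statistical Assumptions). The default is LOCF: "Where data are missing, we will use the Last Observation Carried Forward (LOCF) missing data imputation technique". The reason given is "given that < 30% of data were missing for any particular subject in our prior work". The switch is: "If the proportion of missing data is higher, we will use regression based multiple imputation". The same paragraph adds: "Little's MCAR test (missing completely at random) will be used to test that missingness is in no way related to the intervention".

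**Missing data, SAP** (Statistical Assumptions). The default is different: "Where data are missing, we will substitute the mode for categorical data and the median for continuous data". The reason is "given that <0.5% of data were missing for any measure in our preliminary trial", and the switch is: "If the proportion of missing data is higher, we will use multiple imputation".

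**Outcome model, protocol** (Statistical Analysis). A linear mixed model with a random intercept and a separate slope for each arm, applied to PHQ-9, GAD-7 and grief intensity. The protocol observes: "Mixed models are able to accommodate differing numbers of measurements at varying time intervals for participants". Its assumptions section nevertheless adds time from enrollment to last observation as a covariate.

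**Outcome model, SAP.** The Statistical Analysis prose names mixed models for the same hypotheses in much the same terms. The Statistical Assumptions section, however, calls the comparison a last-observation analysis. The only equation printed regresses the last post-baseline score on study group, baseline score and time since enrollment.

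**Status.** The SAP is dated January 5, 2019. The protocol carries changes dated 9/7/2021 and 6/16/2022. Neither states which takes precedence.

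**The concern.** Two analysts, each following one document faithfully, could fill the same gaps by different methods and fit models that estimate different quantities. With no stated precedence, the choice could be made after the results are seen.

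LOCF sits badly with a slope model. Each carried-forward score adds a flat segment to that caregiver's trajectory and is then treated as if it had been observed. Missing data are expected here: section V of the protocol plans for 30% attrition.

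The protocol's safeguards do not close the gap. Little's test compares observed means across missing-data patterns. A non-significant result does not show that missingness is unrelated to arm, and the test cannot see dependence on scores never collected. Analysis by intention-to-treat fixes who is analysed and in which arm; by itself it does not deal with informative missingness.

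**Working it through.** The plan prints no figure for the effect of missing data, so there is none to reproduce. The planned 468 does not enter steps 1 to 6.

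**1. Do the two rules ever give different instructions?** Suppose 5% of scores on a measure are missing and no subject reaches 30%. The protocol leads to LOCF. The SAP's 0.5% is exceeded, so it leads to multiple imputation. The two percentages differ 60-fold (30 / 0.5) and use different units, subject and measure.

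**2. Can the 30% be applied?** The protocol mentions a subject only when describing prior work. Table 2 lists 5 fixed visits before bereavement and 6 after death. A caregiver who misses days 90 and 150 but attends every bereavement visit is missing:
- 2/5 = 40% within the phase, hence multiple imputation;
- 2/11 = 18% over all fixed visits, hence LOCF.

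Nor is it stated whether multiple imputation then applies to that subject or to everyone.

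**3. LOCF for all missing scores, equal dropout.** Assumptions: visits at days 0, 14, 30, 90, 150 (Table 2); linear trends; 30% permanent dropout unrelated to scores, spread evenly, so 7.5% leave before each follow-up visit. After LOCF the data are balanced, so the fitted slope is Σ(t − t̄)m(t) / Σ(t − t̄)², where m(t) is the average day from which the analysed score comes.
- t̄ = 284/5 = 56.8; Σ(t − t̄)² = 15,564.8.
- m(14) = 0.925×14 = 12.95
- m(30) = 0.85×30 + 0.075×14 = 26.55
- m(90) = 0.775×90 + 0.075×(30 + 14) = 73.05
- m(150) = 0.70×150 + 0.075×(90 + 30 + 14) = 115.05
- Numerator: −42.8×12.95 − 26.8×26.55 + 33.2×73.05 + 93.2×115.05 = 11,882.1.
- Slope retained: 11,882.1 / 15,564.8 = **0.763**.

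Both arms shrink alike, so the slope difference shrinks by the same factor. Simulation (234 per arm, between-person/residual SD 4/2.5 or 3/3, true difference −0.34 per month) agrees: 23–24% too small, with 95% intervals covering the truth in 64–74% of trials. Observed scores alone gave −0.34 and 94–96% coverage.

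**4. LOCF for all, unequal dropout.** The loss is proportional to dropout, so the slope retained is 0.842 at 20% and 0.685 at 40%. Differences are intervention minus control, in points per month; negative favours the intervention.

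| Control slope | True difference | Dropout, intervention / control | After LOCF |
|---|---|---|---|
| −0.45 | −0.34 | 40% / 20% | −0.79×0.685 + 0.45×0.842 = −0.16 |
| −0.45 | −0.34 | 20% / 40% | −0.79×0.842 + 0.45×0.685 = −0.36 |
| +0.45 | −0.145 | 40% / 20% | 0.305×0.685 − 0.45×0.842 = −0.17 |
| −0.45 | 0 | 40% / 20% | 0.45×(0.842 − 0.685) = +0.07 |
| +0.45 | 0 | 40% / 20% | −0.07 |

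The effect can be too small, too large or created from nothing, in either direction.

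**5. LOCF only for subjects under 30%, counted within the phase.** Under permanent dropout, only the 7.5% who miss day 150 alone (1/5 = 20%) are filled by LOCF. Their day-150 score comes from day 90, which lowers m(150) by 0.075×60 = 4.5 days. If multiple imputation is unbiased for the rest, the loss is 93.2×4.5 / 15,564.8 = **2.7%**. Simulation gave 2–3%, with 94–95% coverage.

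**6. Is the printed random-intercept model enough on its own?** Assume individual slopes vary with SD 0.6 per month (variance 0.36) and data are complete. In months, Σ(t − t̄)² = 15,564.8/900 = 17.29. With residual SD 2.5:
- true variance of one person's slope: 6.25/17.29 + 0.36 = 0.721;
- variance the model assumes: (6.25 + 0.36×17.29/4)/17.29 = 0.451.

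The true standard error is √(0.721/0.451) = 1.26 times the reported one, so a nominal 5% test rejects about 12% of the time. With residual SD 3 the ratio is 1.20 and the rate about 10%.

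**The case against.** **Most of the LOCF harm needs a reading that the protocol does not state.** The only unit it names is a subject. On that reading the bias is 2–3%, and where multiple imputation was applied to all outcome scores in simulation it matched the observed-data analysis. This stands, and it limits the size of the problem. It does not justify keeping LOCF, since the protocol leaves the reading open and the model does not need it.

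**Median/mode substitution is unlikely to be reached.** With 30% dropout spread evenly, (7.5 + 15 + 22.5 + 30)/5 = 15% of scores are missing, far above 0.5%. This also stands. The practical conflict is LOCF against multiple imputation.

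**The model conflict lies mainly inside the SAP.** Its prose agrees with the protocol, and neither document labels a primary model. A last-value regression is a legitimate analysis of a different quantity, so preferring the mixed model is partly a choice. What cannot stand is both being offered for the same hypotheses.

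**Stronger inferences that a reader might draw, and that the documents do not support:**
- *LOCF always shrinks the effect.* The third row of the table in step 4 shows otherwise. The documents give no trend, and the protocol's background says that caregiving becomes harder near death, so rising scores are plausible.
- *LOCF gives a type I error of 22–28%.* That arises in simulation only with a 0.45-per-month trend, 40% against 20% dropout and LOCF for everyone. With falling scores nearly all those rejections favour control.
- *The two models would often disagree on significance.* They did so in 20–25% of simulated trials at 0.73 points by day 150, in 1–3% at 1.70, and in none at the 4 points in section V. The first two are the differences detectable at 80% power with 234×0.7 = 163.8 per arm, reading 5.5 as a variance or as an SD.
- *Visits after the patient's death would be filled in.* Table 2 ends the pre-bereavement schedule at transition and makes the wind-down survey the final measure. Those visits are not scheduled.

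**Conclusion.** The concern holds in a limited form. Three points rest on the text alone: the missing-data rules are incompatible and no precedence is stated; the SAP's printed equation and last-observation label contradict its own mixed-model prose and the protocol's slope model; and the 30% has no denominator or scope for this trial.

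LOCF for outcome scores is unnecessary on any reading. Its cost runs from about 2–3% of a true slope difference (subjects under 30% only) to about 24% (all missing scores, equal 30% dropout). With unequal dropout the direction depends on which arm loses more caregivers and whether scores rise or fall. These sizes rest on assumed linear trends, SDs and dropout patterns that neither document gives. This should be fixed before analysis.

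**What to change.** - **(a)** In both documents, name one primary analysis: the mixed model fitted by REML or maximum likelihood to all observed scores, stated to be valid under missing at random. Allow for between-person slope variation through random slopes, an unstructured covariance or robust standard errors, because a random intercept alone can give intervals that are too narrow (step 6).
- **(b)** Label the SAP's last-post-baseline regression secondary. Drop the time-to-last-observation covariate from the mixed model; it belongs to the last-value analysis.
- **(c)** Delete LOCF and median/mode substitution for outcome scores. Keep multiple imputation for missing covariates and mediators.
- **(d)** Add a missing-not-at-random sensitivity analysis, for example delta-adjusted, and report dropout by arm and reason in place of relying on Little's test.
- **(e)** Reissue the SAP to match, and state which document governs.

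The cost is wording in both documents and a little more programming; no new data are needed. The primary result then relies on missing at random, which the sensitivity analysis in (d) is there to probe.
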